It is possible that during the course of the study, certain changes may become desirable, although none are anticipated at this time. All changes to the investigation require prior approval from the investigator's Institutional Review Board (IRB) or Ethics Committee (EC) and if necessary, the FDA. Any other deviation from the stated protocol will be considered as such and will be reported accordingly. Since TSA is an elective procedure, it is not expected that treatment will require administration in an emergency setting, therefore all changes to the protocol require review and approval by the investigator's IRB prior to implementation.

RADIOGRAPHIC PROTOCOL

A detailed radiographic protocol is contained in Exhibit 3.

STATISTICAL ANALYSIS PLAN

This is a two-group, multi-center, randomized single blinded clinical trial to compare Total Shoulder Arthroplasty with Biomet's Comprehensive[®] Shoulder System with nano humeral component to another active intervention, a Total Shoulder Arthroplasty with Comprehensive[®] Shoulder System with mini stem component (abbreviations: Investigational vs. Control).

PRIMARY STATISTICAL HYPOTHESES AND DEFINITION OF STUDY SUCCESS

This study is designed to show that the Investigational device is non-inferior to the control device using three co-primary study endpoints. This will be shown using a closed testing method in which each of the primary endpoints specified below are compared using α =0.05. Study success requires that the Investigational group successfully demonstrate non-inferiority when compared to the Control group for all three of the individual primary endpoints, using the statistical methods described below. Because non-inferiority must be successfully shown for all three endpoints for study success, the type I error rate is preserved at 5% for the entire primary endpoint.¹

The individual non-inferiority hypotheses for each of these three tests are as follows:

Radiographic Success

The proportion of successful outcomes (i.e., patients meeting radiographic success criteria) in the Investigational group is non-inferior to the proportion of successful outcomes in the Control group using a 10% margin of non-inferiority. The test is based on the lower bound of a one-sided 95% confidence interval for the difference, Investigational minus Control, in proportions of success at 22+ months. A conclusion of non-inferiority is supported if the lower bound of the confidence interval is at least -0.10.

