Information on plausible values of the percentage of patients projected to be radiographic failures was found by looking in the literature to find plausible rates for each component of the radiographic failure definition. Subsidence and migration of the humeral component and progressive radiolucency around the humeral component have been reported at approximately 2% and 0%, respectively. Migration of the glenoid component and progressive lucency of the glenoid component have been reported at approximately 5% and 6%, respectively⁶. Because some overlap is to be expected, the overall Radiographic Success rate is estimated to be 93% for sample size calculation purposes.

Assumptions:

α = 0.05	Probability of Type I error
β = 0.10	Probability of Type II error: power = $1 - \beta$
$p_{C} = p_{I} = 0.93$	Estimated success rate for Control and Investigational groups
δ = 0.10	Non-inferiority Margin

⁶ Sperling,et al. "Radiographic assessment of ingrowth total shoulder arthroplasty." *JBJS.* November/December 2000, Vol 9 No. 6, p 507-513.

Resulting sample sizes (number of shoulders), not adjusted for attrition, are 112 Investigational vs. 112 Control (5% type I error rate, 90% power). The sample size was increased by 15% to allow for possible attrition. This gives a sample size of 264 total subjects (132 Investigational and 132 Control).

Absence of Revision/Removal/UADE

Non-inferiority sample size calculations were implemented in nQuery Advisor 7.0 software using a 1:1 ratio of Investigational to Control subjects. This software uses methodology as described in a text by Farrington and Manning⁷.

The sample size needed to obtain 90% power for testing for non-inferiority of the investigational device to the control device with regard to Absence of Revision/Removal/UADE was calculated as follows:

Definitions:

p_I : Proportion of shoulders in the Investigational treatment group without a

Revision/Removal/UADE

 p_C : Proportion of shoulders the Control treatment group without a Revision/Removal/UADE δ : Non-inferiority margin. Lower 95% confidence bound for difference in proportions of clinically successful subjects at 22+ months (Investigational – Control) must be greater than $-\delta$.

For a specified constant, $0 < \delta < 1$, the hypotheses of non-inferiority are:

$$H_0: p_I - p_C \le -\delta vs. \quad H_A: p_I - p_C > -\delta.$$

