Information on plausible values of the percentage of patients with a revision was found in an article by Jost, et. al. on subjects with Biomet Comprehensive mini-stem shoulder device⁸. A

⁷ Farrington and Manning. "Test statistics and sample size formulae for comparative binomial trials with null hypotheses of non-zero risk difference for non-unity relative risk". *Statistics in Medicine* 9(1990) pp 1447-1454.

total of 49 patients underwent shoulder replacements with the TESS humeral prosthesis with minimum follow-up 2 years. One implant was revised, resulting in a revision rate of 2.0%.

Fracture/perforation of bone, joint dislocation, and dissociation of the device have been reported at approximately 2%⁹, 1%¹⁰ ¹¹, and 0¹²% respectively. Fracture/perforation of the device is not expected to occur and so is estimated at 0%, Using this information, overall success rate is estimated to be 95% (2%+2%+1%) for sample size calculation purposes.

Assumptions:

$\alpha = 0.05$	Probability of Type I error
β = 0.10	Probability of Type II error: power = $1 - \beta$
$p_{C} = p_{I} = 0.95$	Estimated success rate for Control and Investigational groups
δ = 0.10	Non-inferiority Margin

Resulting sample sizes (number of shoulders), not adjusted for attrition, are 82 Investigational vs. 82 Control (5% type I error rate, 90% power). The sample size was increased by 15% to allow for possible attrition. This gives a sample size of 194 total subjects (97 Investigational and 97 Control).

⁸ Jost, Patrick et. al. "Total Shoulder Arthroplasty Utilizing Mini-Stem Humeral Componts: Technique and Short-Term Results." *Hospital For Special Surgery Journal* (2011).

⁹ Bohsali, et. al. "Complications of Total Shoulder Arthroplasty." *JBJS.* 2006 Volume 88-A Number 10, p 2279-2292.

¹⁰ Pfahler, et. al. "Hemiarthroplasty versus total shoulder prosthesis: Results of cemented glenoid components." *J Shoulder Elbow Surg* March/April 2006, p 154-163.

¹¹ Boyd, et. al. "Total Shoulder Arthroplasty vs Hemiarthroplasty." *Journal of Arthroplasty*. December 1990, Vol 5 No. 4, p 329-336.

¹² Blevins, et. al. "Dissociation of modular humeral head components: A biomechanical and implant retrieval study." J Shoulder Elbow Surg March 1997, Volume 6 Issue 2, p A1.

American Shoulder and Elbow Surgeons(ASES) Score

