(Radiographic Success,	values until the lower limit of the 95% Confidence interval for the	
Absence of	difference in proportions is equal to the non-inferiority margin	
Revision/Removal))	(the tipping point). Graph will show which imputations of	
Kevision/Kemovaljj	success/failure for the missing values in the investigational and	
	control groups lead to a conclusion of inferiority, and which lead	
	to a conclusion of non-inferiority. Missing Values as Success: Imputation of missing values as	
	"success"	
	Missing Values as Failures: Imputation of missing values as	
	"failure"	
	lanure	
	Last Observation Carried Forward: Missing observations in	
	either group are imputed by taking the most recent outcome prior	
	to 24 months and using it in place of the missing 24-month	
	outcome.	
	2 Year In-Window Analysis : Only data collected within the 2-	
	year per-protocol visit window (22-26 months) are included in	
	this analysis.	
	Multiple Imputation: This method replaces each missing value	
	with a set of plausible values that represent the variability around	
	the choice of which value to impute.	
Continuous	Replace with Maximum: Imputation of missing ASES as "100"	
(ASES Score)		
	Replace with Minimum: Imputation of missing ASES as "0"	
	Last Observation Carried Forward: Missing observations in	
	either group are imputed by taking the most recent outcome prior	
	to 24 months and using it in place of the missing 24-month	
	outcome.	
	2 Year In-Window Analysis : Only data collected within the 2-	
	year per-protocol visit window (22-26 months) are included in	

this analysis.
Multiple Imputation: This method replaces each missing value
with a set of plausible values that represent the variability around
the choice of which value to impute.

In addition, in the event that one or more subjects receive the opposite treatment than the one they were randomized to receive, a sensitivity analysis will be done on patients "as randomized" to make sure it is consistent with the primary analysis ("as treated"). However, because randomization will be performed intra-operatively and the patient must be able to receive either treatment in order to be randomized, this situation is not expected to occur. Other sensitivity analyses will be conducted as needed (i.e. if the effect of missing data on a particular primary outcome is still unclear).

TESTS FOR INTERACTION

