A description of all protocol deviations will be provided. The association between the proportion of subjects with a protocol deviation and device group across investigators will be examined using the Breslow-Day test for homogeneity of odds ratios. Investigators with less than or equal to 3 cases in either treatment will be combined to form a "pooled" investigator for analysis. A significant p-value indicates heterogeneity of odds ratios for the proportion of subjects (Investigational vs Control) with a protocol deviation across investigators, and in this case the proportions of subjects with a deviation will be examined graphically and descriptively by treatment group and site to assess dependency.

DATA COLLECTION

DATA COLLECTION TIME POINTS

Windows for this study will be as follows:

Table 1: Analysis Windows

Interval	Follow-Up Window
	(Days from Surgery)
Preoperative	≤ 0
6 Weeks	28-56
3 Months	78-106
1 Year	304-426
2 Year	669-791
2+ Year	> 791

The principal data collected is described in the following table:

Study Parameter	Data Collected
Demographic and Baseline Measurements	Age, Height, Weight, Gender, Race/Ethnicity, Unilateral/Bilateral, Primary Diagnosis, Prior Treatments, Concomitant Medications
Efficacy Measurements	American Shoulder and Elbow Surgeons (ASES) Score, Constant Score, SANE Score, Radiographic Assessment
Safety Measurements	Revision/Removal, Adverse Events
Study Success Criteria	Study success requires that the Investigational group successfully demonstrate non-inferiority when compared to the Control group for all three of the individual primary endpoints.

Table 2: Principal Study Data

INFERENTIAL METHODS

SIGNIFICANCE LEVELS

The Type I error rate for the primary study analysis will be 0.05.

Comparisons for secondary, exploratory, and safety analyses will use $\alpha = 0.05$, with no adjustment for multiple comparisons. Because no adjustments will be made for multiple

comparisons, secondary, exploratory, and safety endpoints will be reported as exploratory analyses without claims of statistical significance.

SUBJECT ACCOUNTING

Accountability tables will be generated to show, at each study visit, the number of Investigational and Control subjects who might be expected to attend a given visit and the number and proportion who did attend.

The following definitions specify how the subject accountability table tracks subject follow-up for the Control and Investigational arms:

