BASELINE CHARACTERISTICS

Subjects in the Investigational and Control study groups will be compared regarding a list of baseline items, including preoperative ASES and Constant Scores, demographics (age, gender, and primary diagnosis), medical history, and comorbidities.

EFFICACY EVALUATIONS

Primary Endpoint

The confidence intervals used in the analysis of the binary primary endpoints (Radiographic Success and Absence of Revision/Removal/UADE) will be 1-sided, 95% confidence intervals for the difference between proportions in two independent samples. They will be calculated using the Wald method as based on a normal approximation to the binomial, as follows:

$$(p_C - p_I) + z_\alpha \sqrt{SE_C^2 + SE_I^2}$$

Where

 p_{C} = proportion of success in the Control group, p_{I} = proportion of success in the Investigational group, α = 0.05, and

$$SE_C = \sqrt{\frac{p_C(1-p_C)}{n_C}}$$
 and $SE_I = \sqrt{\frac{p_I(1-p_I)}{n_I}}$

The confidence interval used in the analysis of the continuous primary endpoint (ASES Score) will be a 95% confidence interval for the difference between means in two independent samples. They will be calculated using the normal distribution, as follows:

$$(\overline{x}_C - \overline{x}_I) + z_\alpha \sqrt{\frac{s_C^2}{n_C} + \frac{s_I^2}{n_I}}$$

Where

 x_{C} = mean ASES score in the Control group,

 $\overline{x_{I}}$ = mean ASES score in the Investigational group,

 $s_{\scriptscriptstyle C}$ = standard deviation of the ASES scores for the Control group,

 s_{T} = standard deviation of the ASES scores for the Investigational group, and

 $\alpha = 0.05$

Secondary Endpoints

Secondary outcomes include the ASES score, SANE score, Constant score, and radiographic endpoints at 6 weeks, 6 months, 1 year, and 2 years separately. These outcomes will be compared for Investigational and Control groups at each time point.

Exploratory Analyses14

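### The Wald interval for the two binary co-primary endpoints runs at about 5.6% and 5.9–6.0% one-sided error at the plan's own success rates, not the stated 5%

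*Combined protocol and SAP*

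**What the plan says.** The Primary Endpoint part of Efficacy Evaluations prescribes one-sided 95% intervals for the two binary co-primary endpoints: "They will be calculated using the Wald method as based on a normal approximation to the binomial". The printed standard error is unpooled, so each arm contributes its own observed variance. The hypotheses section sets the rule for Radiographic Success: "The test is based on the lower bound of a one-sided 95% confidence interval for the difference, Investigational minus Control, in proportions of success". The bound must be at least -0.10. The same rule applies to Absence of Revision/Removal/UADE.

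Two places state the error rate. Significance Levels says: "The Type I error rate for the primary study analysis will be 0.05". The definition of study success argues that, because all three endpoints must pass, "the type I error rate is preserved at 5% for the entire primary endpoint".

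The Sample Size section supplies the planning rates. For the radiographic endpoint, "the overall Radiographic Success rate is estimated to be 93% for sample size calculation purposes". For revision/removal/UADE, "overall success rate is estimated to be 95% (2%+2%+1%) for sample size calculation purposes". It requires 112 and 82 evaluable shoulders per arm respectively for 90% power at a 10% margin. It enrols 132 per arm after a 15% attrition allowance, and it cites Farrington and Manning for the method. No score or exact interval is planned, even as a sensitivity analysis.

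**The concern.** An unpooled Wald interval for a difference in proportions can be too narrow when success rates are close to 1, as they are here. The error then goes in one direction, towards declaring non-inferiority.

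The all-must-pass argument is sound for multiplicity, but it only caps study-level error at the largest error among the three component tests. It yields 5% only if each component holds 5%. If two of the three do not, the plan's statement about its primary analysis is inaccurate at the plan's own assumptions, and a borderline result could depend on the choice of interval.

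The tipping-point analysis has the same exposure. It fills in "values until the lower limit of the 95% Confidence interval for the" difference reaches the margin, so the choice of bound moves its boundary directly.

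**Working it through.** **Inputs, all from the plan.** Margin 0.10; one-sided α = 0.05 (z = 1.645); power 90% (z = 1.282); success rates 0.93 and 0.95 in both arms; 112 evaluable and 132 enrolled per arm.

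**Reproducing the planned sizes.** The unpooled formula is n = (1.645 + 1.282)² × 2p(1 − p) / 0.10², with (1.645 + 1.282)² ≈ 8.564.
- Radiographic: 8.564 × 2 × 0.93 × 0.07 / 0.01 = 111.5, so 112. Then 112/0.85 = 131.8, so 132.
- Revision/removal/UADE: 8.564 × 2 × 0.95 × 0.05 / 0.01 = 81.4, so 82.

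Both match. The score formula with restricted maximum-likelihood variance would give 128.3 and 102.8 (129 and 103). The sizing is therefore consistent with the Wald test, although Farrington and Manning is cited.

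**Exact error.** Both binomials were enumerated in full with the Investigational rate at control minus 0.10. The Wald rule rejects when (p_I − p_C) − 1.645 × SE ≥ −0.10. The score rule rejects when (p_I − p_C + 0.10) divided by the restricted-MLE standard error is at least 1.645. Power was computed the same way at equal rates.

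| Endpoint (control rate) | n per arm | Wald error | Score error | Wald power | Score power |
|---|---|---|---|---|---|
| Radiographic (0.93) | 112 | 5.55% | 4.89% | 90.2% | 87.6% |
| Radiographic (0.93) | 132 | 5.61% | 5.06% | 93.6% | 91.8% |
| Revision/removal/UADE (0.95) | 112 | 6.01% | 4.94% | 95.9% | 93.7% |
| Revision/removal/UADE (0.95) | 132 | 5.90% | 4.91% | 97.8% | 96.3% |

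A simulation of 2,000,000 trials gave Wald errors of 5.55%, 5.61%, 6.02% and 5.92%, in the same order.

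**Dependence on sample size and rate.** Over equal arms of 82 to 132, Wald error runs 5.4–6.0% (radiographic) and 5.6–6.6% (revision/removal/UADE). The score test runs 4.7–5.1% and 4.5–5.1%. For five unequal splits of 224 shoulders, none more uneven than 105 against 119, Wald error was 5.46–6.23% and 5.61–6.51%. It would reach about 7.1% only with control success near 98%, which the plan does not assume.

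**Study level.** Multiply the error of the endpoint at its margin by the Wald power of the other two at planned rates, assuming independence. ASES power with SD 19 and margin 9.5 is 98.2% at 112 and 99.2% at 132.
- 112 per arm, radiographic at margin: 5.55% × 0.959 × 0.982 = 5.2%.
- 112 per arm, revision/removal/UADE at margin: 6.01% × 0.902 × 0.982 = 5.3%.
- 132 per arm: 5.61% × 0.978 × 0.992 = 5.4%, and 5.90% × 0.936 × 0.992 = 5.5%.

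**What it does to a result (112 per arm).** With 8 control and 12 Investigational failures, the difference is −4/112 = −0.0357.
- Wald: SE = √(0.0714 × 0.9286/112 + 0.1071 × 0.8929/112) = 0.0380, so the bound is −0.0357 − 0.0626 = −0.098, which passes.
- Score: the restricted rates are 0.847 and 0.947, so z = 0.0643/0.0401 = 1.60, which fails. The score test allows 11.

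With 5 control failures the limits are 10 (Wald) and 9 (score). For every control count from 0 to 20, at 112 and at 132, the limits differ by 0 or 1. At the margin and 112 per arm the methods disagree in 0.7% (radiographic) and 1.1% (revision/removal/UADE) of trials.

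**The case against.** The strongest reply concerns proportion. The plan's 5% refers to the whole primary analysis, where the excess is 0.2 to 0.5 points rather than the per-endpoint 0.6 to 1.0. Wald is fully prespecified with its formula, it fits the sizing, and it leaves the analyst no discretion. At 112 per arm the two methods have the same cut-off at many control counts, including 6, 7, 9, 10 and 11. The score test is itself approximate (5.06% for the radiographic endpoint at 132), so it does not guarantee 5% either, and it costs 2.6 points of radiographic power at 112. One could keep Wald, add a score bound as a sensitivity analysis and call 5% nominal.

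Most of this stands as a limit on severity: the excess is modest, the sizing is coherent and nothing is left undefined. It does not remove the point. Study-level error is still above 5% under the plan's own assumptions. The per-endpoint figures are the relevant ceiling when the other endpoints are nearly certain to pass. The Wald excess is also present at every equal arm size from 82 to 132, whereas the score test stays within about half a point of 5%. Better calibration, not an exact guarantee, is what is claimed for it.

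**Conclusion.** The concern holds and should be fixed. At control success of 93% and 95%, the Wald rule has exact one-sided error of about 5.6% and 5.9–6.0% at 112 to 132 per arm, against a stated 5%. Study-level error is 5.2–5.5%, assuming independent endpoints and planned rates for the two not at their margin. The exact values move with the evaluable numbers and rise with the control success rate. The practical effect is at most one Investigational shoulder at the cut-off. This is a calibration fault rather than a fatal flaw, but the 5% statement is inaccurate as written, and changing the method means the power statement must change too.

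**What to change.** For both binary co-primary endpoints and the binary tipping-point analysis, specify the Farrington–Manning or Miettinen–Nurminen score one-sided 95% lower bound for Investigational minus Control, compared with −0.10. Keep Wald as a sensitivity analysis. Make the change before any unblinded analysis, so that the choice of method cannot look driven by results.

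Restate power under the score test: radiographic 87.6% at 112 evaluable per arm and 91.8% at 132; revision/removal/UADE 93.7% and 96.3%. State that 90% radiographic power needs at least 124 evaluable per arm (89.7% at 123, 90.6% at 124).

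The cost is SAP wording and standard software, plus real power. With 132 enrolled, 90% radiographic power survives only if no more than 132 − 124 = 8 per arm (6.1%) are unevaluable. Keeping the 15% allowance would need 124/0.85 = 146 per arm, 14 more than planned. The sponsor may accept 87.6% at the planned attrition or enrol more, but should say which.

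One drafting correction: the Primary Endpoint formulas are printed as Control minus Investigational plus z × SE, and the ASES interval is not called one-sided there. This mirrors the hypotheses section and gives the same decision against +0.10 or +9.5. For consistency, write all three as (Investigational − Control) − 1.645 × SE, one-sided, compared with −0.10 or −9.5, using the score bound in place of this form for the binary primary tests.

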Absence of Revision/Removal/UADE

¹ Dmitrienko, Alex, et al. *Analysis of Clinical Trials Using SAS.* SAS Publishing, 2005, pp75-76.

The proportion of successful outcomes (i.e., patients not requiring a revision/removal of any device component or receiving a UADE during the course of the study) in the Investigational group is non-inferior to the proportion of successful outcomes in the Control group using a 10% margin of non-inferiority. The test is based on the lower bound of a one-sided 95% confidence interval for the difference, Investigational minus Control, in proportions of success at 22+ months. A conclusion of non-inferiority is supported if the lower bound of the confidence interval is at least -0.10.

American Shoulder and Elbow Surgeons Score

The mean American Shoulder and Elbow Surgeons (ASES) Score for the Investigational group is non-inferior to the mean ASES score for the Control group using a 9.5-point margin of noninferiority. This margin is based on an approximation that is sometimes used for the MCID based on the observation that for many patient-reported outcome measures, the MCID is about half the SD of change². This method is mentioned as well in an article by Singh et. al, where a half-standard deviation is mentioned as a generally accepted clinically significant benchmark³. Information about plausible values of the standard deviations ASES scores are available in an article by Angst, et. al.⁴ This article gives a standard deviation of postoperative ASES score for 142 subjects of 19.0 points, giving a half-standard-deviation of 9.5 points.

This test will be based on the lower bound of a one-sided 95% confidence interval for the difference, Investigational minus Control, in means at 22+ months. A conclusion of non-inferiority is supported if the lower bound of the confidence interval is at least -9.5 points.

RANDOMIZATION DETAILS

Study: Comprehensive® nano

² Murray et al. "The use of the Oxford hip and knee scores." *JBJS(Br)*. 2007; 89-B 1010-14.

³ Singh, Jasvinder et. al. "Challenges with health-related quality of life assessment in arthroplasty patients: Problems and solutions". *J Bone Joint Surg* 2010; 18:72-82.

⁴ Angst et. al. "Responsiveness in Shoulder Arthroplasty Outcome Instruments." Arthritis & Rheumatism (Arthritis Care & Research) Vol. 59, No. 3, March 15, 2008, pp 391–398

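### The printed formulas for the primary confidence bounds run Control minus Investigational, while the success rules need the lower bound of Investigational minus Control, and no threshold is given for the reversed form

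*Combined protocol and SAP*

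**What the plan says.** The SAP section on primary statistical hypotheses and study success sets one rule per endpoint. For Radiographic Success and for Absence of Revision/Removal/UADE the test uses the "lower bound of a one-sided 95% confidence interval for the difference, Investigational minus Control, in proportions of success at 22+ months", and "A conclusion of non-inferiority is supported if the lower bound of the confidence interval is at least -0.10". For ASES the direction and side are the same, and "A conclusion of non-inferiority is supported if the lower bound of the confidence interval is at least -9.5 points". The sample size section repeats this direction in the formal hypotheses for each endpoint: the null is Investigational minus Control at or below minus the margin.

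The calculation is given only under Efficacy Evaluations, Primary Endpoint. The binary intervals are described as "1-sided, 95% confidence intervals for the difference between proportions in two independent samples", with no direction in words, and the formula is "p_C - p_I) + z_\alpha \sqrt{SE_C^2 + SE_I^2". The ASES formula is "x}_C - \overline{x}_I) + z_\alpha \sqrt{\frac{s_C^2}{n_C} + \frac{s_I^2}{n_I". Both subtract Investigational from Control and add the z term. Alpha is given as 0.05, but z_alpha is not defined as a number, and the expressions are not labelled as upper or lower bounds. No section states a threshold for Control minus Investigational.

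**The concern.** A non-inferiority rule has three parts that must agree: the direction of the difference, the side of the bound, and the sign of the threshold. Here the rule fixes all three one way, and the formula reverses the direction and carries a plus sign. An analyst has to depart from either the printed formula or the printed threshold to get a valid test, and the plan does not say which.

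The same mismatch affects all three co-primary endpoints, and study success requires all three. If the printed value were programmed straight into the printed rule, the rule would become easier to meet the worse the investigational device performed.

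**Working it through.** **Inputs.** Binary margin 0.10, ASES margin 9.5 and one-sided 95% bounds (primary hypotheses section); alpha 0.05 (Significance Levels); assumed success of 93% and 95% in both arms, ASES SD 19, and 112 evaluable shoulders per arm for the radiographic endpoint (Sample Size Calculation). z = 1.645 for one-sided 0.05 and 1.282 for 90% power.

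**The plan's own sample sizes reproduce.** (1.645 + 1.282)² is about 8.56.
- Radiographic: 8.56 × 2 × 0.93 × 0.07 / 0.10² = 111.5, so 112 per arm.
- Revision/Removal/UADE: 8.56 × 2 × 0.95 × 0.05 / 0.10² = 81.4, so 82.
- ASES: 8.56 × 2 × (19/9.5)² = 68.5, so 69 by the normal formula; the noncentral t gives 70 (power 0.903).
- Dividing by 0.85 for attrition gives 132, 97 and 83.

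All match the plan, so its design calculation uses a one-sided 5% test with these margins.

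**Algebra.** Required bound: L = (p_I − p_C) − 1.645 × SE. Printed expression with z = +1.645: U = (p_C − p_I) + 1.645 × SE. So U = −L for every data set. The rule L ≥ −0.10 is therefore the same as U ≤ +0.10. It is not the same as U ≥ −0.10. The ASES formulas behave identically with 9.5.

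**Illustration, binary.** Nano 80%, control 95%, 112 per arm (rates chosen for illustration):
- SE = √(0.80 × 0.20/112 + 0.95 × 0.05/112) = 0.0430, and 1.645 × SE = 0.071.
- Printed expression: 0.15 + 0.071 = +0.221. Required bound: −0.15 − 0.071 = −0.221.
- The required bound fails against −0.10. The printed value would pass if compared with −0.10, and fails correctly if compared with +0.10.

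**Illustration, ASES.** Nano 15 points worse, SD 19, 112 per arm: SE = 19 × √(2/112) = 2.54 and 1.645 × SE = 4.18. The printed expression is +19.2 and the required bound is −19.2, with the same pattern against −9.5 and +9.5.

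**Probability of passing,** by exact enumeration of two binomials, 112 per arm, control 93%:

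| Nano success | Required bound vs −0.10 | Printed value vs +0.10 | Printed value vs −0.10 |
|---|---|---|---|
| 93% | 0.902 | 0.902 | 1.000 |
| 83% (at the margin) | 0.055 | 0.055 | 1.000 |
| 73% | 0.0001 | 0.0001 | 1.000 |

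The second and third columns agree, as the algebra says. The last column shows what happens only if formula and threshold are joined without changing the sign. That combination can also fail a better device: control 80% and nano 100% gives −0.20 + 1.645 × 0.0378 = −0.138, below −0.10.

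**The case against.** A reader might infer that the plan as written will pass an inferior device. The documents do not support that. The success rules name their own quantity, the lower bound of Investigational minus Control. The Efficacy Evaluations section neither calls its expression a lower bound nor ties it to −0.10 or −9.5. Putting the printed value into the rule would breach the rule's own wording. Three prose rules and three sets of hypotheses agree on direction, against two formula lines. The printed expression is also the correct test in mirror image, and a program that passed every scenario would probably be noticed.

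A reader might also take z_alpha as the lower-tail value −1.645, which would turn the formula into a test of whether control is non-inferior to nano (+0.079 in the binary illustration). With a plus sign and alpha of 0.05 the upper-tail value is the natural reading, and the other contradicts every stated hypothesis.

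These arguments limit the consequence; they do not remove the mismatch. The formulas reverse the difference, z_alpha has no stated value, and the thresholds that would make the formulas work appear nowhere. Damage from PDF extraction is an unlikely explanation, because both formulas show the same orientation.

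**Conclusion.** The concern holds as a specification error in the primary analysis. The formulas and the success thresholds do not match for any of the three co-primary endpoints, and the plan leaves the analyst to reconcile them. With z = +1.645 the printed expression is exactly minus the required bound, so the intended test is recovered against +0.10 or +9.5. A wrong conclusion follows only if the printed value is compared directly with −0.10 or −9.5; in that case even a device 20 percentage points worse would pass with probability 1.000.

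The design is not at fault: hypotheses, margins, error rate and sample size all use the right direction. The illustrative success rates and ASES deficit are assumptions, not forecasts, and 112 per arm is the plan's evaluable number for the radiographic endpoint.

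**What to change.** Preferred: replace the two formulas under Efficacy Evaluations, Primary Endpoint, with
- (p_I − p_C) − 1.645 × √(SE_I² + SE_C²)
- (x̄_I − x̄_C) − 1.645 × √(s_I²/n_I + s_C²/n_C)

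and label each a one-sided 95% lower bound, to be compared with −0.10 and −9.5.

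Equivalent: keep the printed formulas, define z_alpha = +1.645, label them one-sided 95% upper bounds for Control minus Investigational, and state that non-inferiority requires a value of at most +0.10 or +9.5.

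Either version should also call the ASES interval one-sided, since this section says only 95%, and should give the direction and side of the interval used in the tipping-point analysis. The cost is two formula lines and their labels. Sample size, margins and data collection do not change. With either version the radiographic test has power 0.902 at 93% in both arms and a pass probability of 0.055 at the margin (93% vs 83%). The change should be made before outcome data are compared by arm.
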